Poliovirus type 3 response rates compared between Study Group 1 and Study Group 2 AND each lower bound of 95% one-sided confidence intervals for the A/H1N1, A/H3N2, and B response rates after 2 doses compared between Study Group 1 and Study Group 3 is greater than -10%. A study with at least 680 subjects completed in each treatment group would provide 98% power to demonstrate that a treatment with a true response rate of 55%, is non-inferior to a reference treatment with a true response rate of 55%, on a 10% criterion for non-inferiority. The simultaneous evaluation of six independent comparisons, each with 98% probability of success, provides an overall probability of success greater than 90%. The planned enrolment will provide at least 90% power to demonstrate non-inferiority of co-administration compared to separate administrations (at least one month apart) of liquid CAIV-T and OPV based on response criteria for antibody levels to three polio antigens and three influenza virus strains.

The proportion of responders for concomitant administration of CAIV-T and OPV

(Group 1) will be compared with the immune response to polio antigens in Group 2 and the immune response to influenza antigens in Group 3. The non-inferiority evaluation will be based on exact 90% two-sided confidence intervals for the six differences in proportions . If the lower limit of the confidence interval ** of $\frac{\text{co-admin}}{\text{reference}}$ is $\geq -10\%$ for polio antigen Types 1, 2, and 3 and for influenza strains A/H1N1, A/H3N2 and B, then the null hypothesis of inferiority with respect to a 10% criterion will be rejected at $\alpha=0.05$. StatXact will be used to determine the exact confidence interval. In a secondary analysis the comparison between co-administration and separate administration regimens will be based on the antibody titre (polio) or the titre ratio to baseline (influenza) expressed on a logarithmic scale. The t-test of the mean difference (in log) will be used to form the 90% confidence interval. The estimated difference and the confidence interval will then be exponentiated to obtain the GMT (geometric mean titre, polio) or GMR (geometric mean ratio, influenza) ratio (co-admin./reference) and its 90% confidence interval. If the lower limit of each confidence interval is ≥ 0.5 , the null hypothesis of inferiority with respect to a two-fold criterion will be rejected at $\alpha=0.05$.

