Each of the six immune responses will be evaluated at level of 0.05. The overall level for the six tests remains <0.05 as the null hypotheses for the six tests are required to be rejected simultaneously in order to demonstrate the acceptability of responses of co-administration.

Subjects who were immunised per protocol with blood samples drawn per protocol will be included in the immunogenicity analysis. Specifically, subjects must meet the following criteria to be included in the immunogenicity analysis:

-- The first blood draw (Pre Dose 1) must have occurred at the day of the first dose but prior to the first dose.

-- Time interval between the first and second doses must be 35 + 7 days.

- The second blood draw (Post Dose 1) must have occurred at the day of the second dose but prior to the second dose.
- Time interval between the second dose and the third blood draw (Post Dose 2) must be 35 + 7 days.

Influenza Seronegative Baseline Population – defined for each influenza strain: Those subjects of the immunogenicity evaluable population who had baseline titres for serum A/H1N1, A/H3N2, or B HAI less than or equal to 1:4.

Immunogenicity All Available Population: Subjects who received at least one dose of the assigned treatment and had a pre-dose and post-dose evaluation of serum antibodies.

Safety Population: Subjects who received at least one dose of the assigned treatment.

The demographic data, including gender, and age at each dose, of the immunogenicity and safety analysis populations will be summarised. Baseline serum antibody levels will be reported and the subject definition for seronegative baseline will be applied as a grouping criterion for some immunogenicity outcome summaries.

The primary measure of immunogenicity will be:

- Poliovirus types 1, 2, and 3 by virus neutralisation assay;
- Influenza virus strains A/H3N2, A/H1N1, and B by hemagglutination inhibition assay (HAI). OPV immune response for each poliovirus type is measured at the end of study by 1:10 or greater virus neutralisation assay titre.

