CAIV-T immune response for each virus strain is measured at the end of study by an increase from baseline HAI of four-fold or greater. The primary endpoint for immunogenicity is the proportion of subjects achieving a post-vaccination serum antibody response (as defined above) for each antigen component of OPV and CAIV-T. The primary analysis interval for influenza strains A/H1N1, A/H3N2, and B is one month following the second intranasal vaccination. The primary analysis interval for poliovirus types 1, 2, and 3 is one month following the single dose of OPV.

The secondary endpoint for immunogenicity is the titre of serum antibody for each antigen component of OPV and the titre ratio to baseline of serum antibody to each virus strain of CAIV-T obtained 1 month after vaccination.

The primary analysis interval for influenza strains A/H1N1, A/H3N2, and B is one month following the second intranasal vaccination. The primary analysis interval for poliovirus types 1, 2, and 3 is one month following the single dose of OPV.

The safety objective is to assess the safety and tolerability of CAIV-T in healthy children aged 6 to less than 36 months.

The reactogenicity adverse events are:

Fever (axillary temperature > 37.5°C); Cough; Runny nose or nasal congestion; Irritability; Vomiting; Decreased activity; and Decreased appetite.

The proportion of subjects with any reactogenicity event reported and with other adverse events on any day during the 11-day period following each dose of CAIV-T or placebo will be evaluated. Serious adverse events occurring within 42 days of the first or second vaccination will be listed and summarised.

The overall incidence of reactogenicity events will be compared between the individual CAIV-T groups and the combined Placebo groups using two-sided Fisher's Exact Test. Exact 95% confidence intervals about reactogenicity adverse event frequency differences will be reported. The frequency of other adverse events will be separately compared between subjects randomised to CAIV-T or Placebo using two-sided Fisher's Exact Test.

Ethical Assurance for Protection of Human Rights

Describe in the space provided the justifications for conducting this research in human subjects. If the study needs observations on sick individuals, provide sufficient reasons for using them. Indicate how subject's rights are protected and if there is any benefit or risk to each subject of the study.

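### The secondary titre comparisons leave out the baseline titre for polio and use it inefficiently for influenza, at some cost in precision but not in validity

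*Protocol*

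**What the plan says.** The Data Analysis section of the protocol fixes the secondary immunogenicity comparison in some detail. The comparison "will be based on the antibody titre (polio) or the titre ratio to baseline (influenza) expressed on a logarithmic scale". The method follows: "The t-test of the mean difference (in log) will be used to form the 90% confidence interval". The difference and its limits are exponentiated to a GMT ratio (polio) or GMR ratio (influenza). If each lower limit is at least 0.5, "the null hypothesis of inferiority with respect to a two-fold criterion will be rejected".

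The endpoint definition later in the same section agrees: "The secondary endpoint for immunogenicity is the titre of serum antibody for each antigen component of OPV", with the titre ratio to baseline for each influenza strain. No covariate is named for either.

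The baseline value is available. Research Design and Methods plans a blood sample before the first dose in every child, for both HAI and polio neutralisation. The per-protocol immunogenicity criteria require it: "The first blood draw (Pre Dose 1) must have occurred at the day of the first dose but prior to the first dose". Its other stated uses are descriptive reporting, the four-fold-rise criterion for influenza, and a seronegative-baseline population that is defined for influenza strains only.

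**The concern.** The polio comparison is made in children who, under the Inclusion Criteria, have all had three OPV doses. Their pre-dose titres should therefore vary widely and probably predict the post-dose titre. Comparing post-dose titres alone leaves that variation in the error term, and any chance difference in baseline goes straight into the GMT ratio.

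The titre analysis also matters more for polio than its secondary rank suggests. The primary polio criterion is a post-vaccination titre of 1:10 with no baseline condition. A child already above 1:10 counts as a responder whether or not the study dose had any effect. The background section cites median seroconversion after three doses of 72%, 95% and 65% for types 1, 2 and 3, so many children probably start above that level. The titre comparison is the only planned between-group analysis that could show a weaker polio response in them.

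For influenza the ratio to baseline is a change score: baseline is used, but with its slope fixed at 1. When the correlation between pre and post log titres is below 1 and the SDs are equal, this over-corrects.

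**Working it through.** **Inputs from the protocol.** 680 completers per group; one-sided 0.05 per antigen (90% two-sided interval); two-fold margin, log10(2) = 0.301; 1:1:1 allocation.

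**Inputs that must be assumed.** The correlation r between log baseline and log post-vaccination titre (0.3 to 0.7), the log10 SD (0.4 to 1.0), and equal pre and post SDs. The documents give none of these.

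**The plan's own figure.** The only power stated is for the primary response rates: "A study with at least 680 subjects completed in each treatment group would provide 98% power" at 55% in both groups with a 10-point margin.
- SE = sqrt(2 × 0.55 × 0.45 / 680) = 0.0270.
- Power = Φ(0.10/0.0270 − 1.645) = 0.980, so it reproduces.
- Enrolment: 680/(1 − 0.15) = 800 per group, which also reproduces.

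No power is stated for the titre analysis.

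**Relative variance of the group difference** (post-only t-test = 1):
- ratio-to-baseline t-test: 2(1 − r)
- adjustment for baseline (ANCOVA): 1 − r²
- ANCOVA against ratio to baseline: (1 − r²)/[2(1 − r)] = (1 + r)/2

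| r | Polio: ANCOVA / t-test | Polio cut | Influenza: ANCOVA / ratio t-test | Influenza cut | Ratio t-test / post-only |
|---|---|---|---|---|---|
| 0.3 | 0.91 | 9% | 0.65 | 35% | 1.4 |
| 0.5 | 0.75 | 25% | 0.75 | 25% | 1.0 |
| 0.7 | 0.51 | 49% | 0.85 | 15% | 0.6 |

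Below r = 0.5 the ratio to baseline is noisier than the post-vaccination titre alone.

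**Width of the interval.** At SD 0.8 and r = 0.5:
- Unadjusted SE = 0.8 × sqrt(2/680) = 0.0434, and 10^(1.645 × 0.0434) = 1.179-fold either side.
- With ANCOVA the SE is multiplied by sqrt(0.75) = 0.866, giving 1.153-fold.

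**Chance imbalance (polio).** At SD 0.8 the SE of the baseline difference is also 0.0434. An imbalance of 1.96 SE is 0.085 log10. With slope 0.5 to 0.7 it moves the unadjusted GMT ratio by 10^0.0425 to 10^0.0595, about 10% to 15%.

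**Power against the two-fold margin.** Power = Φ[(log10(true ratio) + 0.301)/SE − 1.645].
- True ratio 1, SD 0.4 to 1.0, r = 0.3 to 0.7: at least 0.998 with or without adjustment.
- True ratio 0.7, r = 0.5 (where post-only and ratio t-tests have equal variance):

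| log10 SD | t-test | ANCOVA |
|---|---|---|
| 0.6 | 0.998 | >0.999 |
| 0.8 | 0.958 | 0.988 |
| 1.0 | 0.853 | 0.929 |

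- For the last row: SE = 1.0 × sqrt(2/680) = 0.0542; (−0.155 + 0.301)/0.0542 − 1.645 = 1.05, so 0.853. With SE × 0.866 = 0.0470 the argument is 1.47, so 0.929.
- Influenza at true ratio 0.7, SD 1.0 and r = 0.3: 0.736 with the ratio t-test, 0.881 with ANCOVA.

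**The case against.** The strongest reply is that nothing here is invalid. Under 1:1:1 randomisation both t-tests estimate the group difference without bias and hold the type I error, and the confidence interval already allows for chance imbalance. That stands.

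The practical effect is also small. The margin is two-fold, there are about 680 children per group, and the titre analysis is not part of the six-comparison success criterion. A shift of 10% to 15% from an unusually large imbalance is modest against a factor of two. That stands too.

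Four stronger readings are tempting, and the documents do not support them:
- A reader might infer that baseline is ignored for all six antigens. It is left out only for polio; the influenza ratio contains it in every value.
- A reader might take the pre-dose polio titre to be the dominant predictor. Three earlier doses make a strong correlation plausible, but no figure is given, and at r = 0.3 the polio variance falls by only 9%.
- A reader might carry the argument about children already above 1:10 over to influenza. The influenza responder criterion is a four-fold rise, so it does not apply there.
- A reader might expect the conclusion against 0.5 to be at risk in general. It is not unless interference is real and the SD is large.

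Two further replies carry part weight. Influenza baselines may pile up at the assay floor (the plan defines a group at or below 1:4), which makes a single slope and the formula gain less certain. And a SAP, not shown, could add a covariate; but the protocol names the t-test, so this is a stated choice rather than a detail left open.

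**Conclusion.** The point holds as a matter of efficiency. The protocol fixes an analysis that discards the baseline titre for polio and gives it a fixed slope of 1 for influenza, although the pre-dose sample is required for every child in the per-protocol immunogenicity analysis. The cost is wider intervals than the data allow and, for polio, a GMT ratio that carries chance baseline imbalance.

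The size rests on assumed correlations and equal SDs: a variance excess that adjustment would remove of 9% to 49% for polio (rising with r) and 35% to 15% for influenza (falling with r) over r = 0.3 to 0.7. The non-inferiority conclusion would rarely differ. The main benefit is a tighter reported ratio, with extra power only when some interference is present and titres are very variable. This is a low-priority improvement to a secondary analysis, with the three polio comparisons first.

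**What to change.** In the Data Analysis section, replace the t-test sentence by a linear model for each of the six antigens: log post-vaccination titre on treatment group and log baseline titre, with country as an optional further term. Exponentiate the adjusted group difference and its 90% confidence interval and apply the same 0.5 limit. For influenza the adjusted difference in log post-vaccination titre takes the place of the GMR ratio as the estimate compared with 0.5. The t-test can stay as a supporting analysis.

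Specify this before the code is opened, since a choice of adjustment made afterwards would be open to challenge. The cost is a sentence or two of text. No new samples or assays are needed, and the SAS or SPSS already planned can fit the model. The gain is less certain where influenza baselines cluster at the assay floor, which is a further reason to put polio first.

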- known or suspected disease of the immune system or those receiving immunosuppressive therapy, including systemic corticosteroids (see corticosteroid section below)
- received any blood products, including immunoglobulin, in the period from six months prior to vaccination through to the conclusion of the study

RECEIVED 1 OCT 2004

A-040652

- There is intent to administer any other investigational vaccine or agent from one month prior to enrolment through to the conclusion of the study
- there is an immunosuppressed or an immunocompromised individual living in the same household
- at any time prior to entry into this study, received a dose of any influenza vaccine (commercial or investigational)
- a documented history of hypersensitivity to egg or egg protein or any other component of the assigned study vaccine
- received aspirin (acetylsalicylic acid) or aspirin-containing products in the two weeks prior to vaccination or for which use is anticipated during the study
- any medical conditions that in the opinion of the Investigator might interfere with interpretation of the study results.

If any of these criteria are met following enrolment, the subject will be excluded from subsequent vaccine dosing.

Definition of Corticosteroid Use

For the purposes of this clinical trial, corticosteroid use as defined by the committee of Infectious Diseases of the American Academy of Pediatrics, The Red Book 40, will meet the exclusion criterion. The Red Book text concerning this is as follows:

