-- Administer assigned intranasal study treatment. The appropriate study personnel must update vaccine accountability records.

-- After vaccination, observe each subject for a minimum of 60 minutes. Emergency management supplies (AMBU bag, adrenaline [epinephrine], and antihistamines) will remain available for initial treatment of an allergic reaction if needed. Record any local reactions or systemic events on adverse event pages in the CRF.

-- Initiate home visits by the FRA as described above, beginning with the afternoon of the immunisation day.

-- The parent(s)/legal guardian(s) are asked to contact the FRA or field clinic immediately if any significant illness or hospitalisation occurs during the study period.

-- Any subject with a clinically significant event (e.g., high fever, convulsion, etc) should be evaluated immediately by a study physician.

-- Serious adverse events (SAEs) data, regardless of causality, will be collected up to study completion. All treatment and associated costs will be provided by the study, as described above.

-- Record all information in the appropriate source documents, and complete the CRF.

Study Visit Three, Study Termination

This visit occurs 35 (+/- 7) days after the second dose of assigned study vaccine. Surveillance staff will contact the parent/guardian and arrange for this visit to the clinic or arrange for the visit with blood collection to occur at home.

- Review subject data from the last visit.
- Obtain and record interim medical history since the last study visit (visit two). Obtain and record all adverse events and concomitant medications between Day 0 and Day 10 following second dose of assigned study treatment (see section 6.2).
- Collect approximately 5 ml of blood for immunogenicity testing.
- Serious adverse events (SAEs) data, regardless of causality, will be collected up to study completion. Any SAE ongoing at study termination must be followed until resolution.
- Record all information in the appropriate source documents, and complete the CRF.

VACCINE ADMINISTRATION

Vaccine to be Administered

At study Visit 1, each enrolled subject will receive either intranasal CAIV-T, or saline placebo, and may concomitantly receive OPV, as assigned. At Study Visit 2, the subject will receive the same intranasal study treatment that he/she received at Visit 1, but no oral treatment. The time interval between Dose 1 and Dose 2 will be 35 (+/- 7) days.

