The multidimensional comparison of primary interest is (1) to evaluate non-inferiority of the serum antibody response to OPV following concomitant administration with CAIV-T relative to the response to OPV administered separately temporally (at least 1 month apart) from CAIV-T and (2) to evaluate non-inferiority of the serum antibody response to CAIV-T following concomitant administration with OPV relative to the immune response of CAIV-T administered separately temporally (at least 1 month apart) from OPV. The response criterion for each viral strain of CAIV-T is a four-fold increase from baseline titre in the hemagglutination inhibition assay (HAI) for influenza virus strains A/H3N2, A/H1N1, and B. The response criterion for each antigen component of OPV is a post-vaccination titre of 1:10 for Poliovirus types 1, 2, and 3 by virus neutralisation assay. The primary analysis interval for influenza strains A/H1N1, A/H3N2, and B is one month following the second intranasal vaccination. The primary analysis interval for poliovirus types 1, 2, and 3 is one month following the single dose of OPV. The primary analysis endpoint will be achieved if lower limits of six independent 95% one-sided confidence intervals for differences in response rates are each greater than -10%.

It is expected that approximately 2,400 subjects will be enrolled in at multiple study sites. Determination of the appropriate sample for this study is dependent on the following assumptions:

-- Loss to follow-up is not greater than 15%.

-- Post-dose 2 influenza antibody response rates, measured as a four-fold or greater increase from baseline serum hemagglutination assay (HAI) will be similar to those observed in earlier studies of CAIV- T, ranging from 48% to 68% for the three strains □ Immune response rates for OPV measured at the end of the study by 1:10 or greater

virus neutralisation assay titres for Poliovirus types 1, 2, and 3 will be similar to those observed in earlier studies of OPV and may be as low as 75%.^{32,36}

-- The co-administration of CAIV-T with OPV will be demonstrated not to interfere with immune response to poliovirus and co-administration of OPV with CAIV-T will be demonstrated not to interfere with immune response to CAIV-T if each lower bound of 95% one-sided confidence intervals for the Poliovirus type 1, Poliovirus type 2, and

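### One per-protocol list for all six antigens drops children from the primary polio comparisons for a missed dose 2 or Visit 3, although their polio endpoint is already complete at Visit 2

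*Protocol*

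**What the plan says.** The Data Analysis section introduces its evaluability list with "subjects must meet the following criteria to be included in the immunogenicity analysis" and makes no distinction between polio and influenza. The list has four entries. The first is a baseline draw on the day of dose 1, before dosing. The other three depend on dose 2:

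- dose 2 has to follow dose 1 by 35 ± 7 days;
- for the post-dose-1 sample, the rule reads "The second blood draw (Post Dose 1) must have occurred at the day of the second dose but prior to the second dose";
- the Visit 3 sample has to follow dose 2 by 35 ± 7 days.

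(The list prints a plus sign in both windows; it is read here as ±, as in the visit schedule.)

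The same section sets the polio time point: "The primary analysis interval for poliovirus types 1, 2, and 3 is one month following the single dose of OPV". OPV is given only at Visit 1. Under Vaccine to be Administered: "At Study Visit 2, the subject will receive the same intranasal study treatment that he/she received at Visit 1, but no oral treatment". Polio is compared between Groups 1 and 2, and influenza between Groups 1 and 3.

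Children without dose 2 are foreseen. The Exclusion Criteria end with "If any of these criteria are met following enrolment, the subject will be excluded from subsequent vaccine dosing", and the Withdrawal criteria ask that such children still be bled where possible. The sample size assumes "Loss to follow-up is not greater than 15" percent.

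Two sentences in Data Analysis point the other way on timing. One is in the sample-size assumptions and one is in the definition of the primary measure. Both place the polio measurement at the close of the study.

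**The concern.** At the Visit 2 draw, about 35 days after OPV, the primary polio endpoint is complete. What follows is an intranasal spray without OPV and a blood draw that the primary polio interval does not use. The list nevertheless makes inclusion in the polio analysis depend on both. Two kinds of child are removed despite a usable polio result:

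- (a) a child bled in window at Visit 2 but not given dose 2;
- (b) a child bled and dosed on time at Visit 2 whose Visit 3 draw is missed or out of window.

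Group 2 shows the mismatch most clearly. Its second dose is saline, and polio is the only primary comparison it enters. A Group 2 child can leave that comparison for missing a placebo spray, or a later sample that no primary comparison involving Group 2 uses.

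At stake are some precision in three of the six co-primary comparisons and the principle that post-randomisation exclusions in a non-inferiority comparison should be no wider than the endpoint needs.

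**Working it through.** **Inputs from the protocol.** 800 per group; loss at most 15%; 680 completers per group; margin 10 points; one-sided 0.05 per antigen (90% two-sided interval); design response 55% in both arms; polio response possibly as low as 75%.

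**The plan's own figure.** Power = Φ(0.10/SE − 1.645), with SE = √(2p(1−p)/n). For p = 0.55 and n = 680, power is 98.0%, which matches the stated 98%. Also 800 × 0.85 = 680.

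**Which criteria the polio endpoint needs.**

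| Criterion | Role for polio at one month after OPV |
|---|---|
| Baseline draw on the day of dose 1 | Retain |
| Dose 1 to dose 2 interval 35 ± 7 days | Only jointly with the next row: fixes the post-OPV sample at 28–42 days |
| Second draw on the day of dose 2, before it | As above; fails automatically if dose 2 is not given |
| Third draw 35 ± 7 days after dose 2 | None |

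The two middle criteria serve a purpose for polio, but they express it through dose 2 and not through the OPV dose.

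**How many children.** The protocol gives neither count, so both are assumptions.

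- (a) If 0.5% to 2% are barred from dose 2 but attend Visit 2: 800 × 0.005 = 4 to 800 × 0.02 = 16 per arm. This is an upper figure for what the fix would recover, because children barred for blood products or immunosuppressants would stay excluded.
- (b) Allowed loss is 800 × 0.15 = 120 per arm. If a quarter, half or three quarters falls after Visit 2, then 30, 60 or 90 per arm have the polio sample but fail the Visit 3 criterion.

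**Effect of (b) on each polio comparison at p = 0.75.** Half-width = 1.645 × SE.

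| n per arm | SE | 90% half-width (points) | Power |
|---|---|---|---|
| 680 | 0.02348 | 3.86 | 99.55% |
| 710 | 0.02298 | 3.78 | 99.66% |
| 740 | 0.02251 | 3.70 | 99.74% |
| 770 | 0.02207 | 3.63 | 99.81% |
| 800 (ceiling) | 0.02165 | 3.56 | 99.85% |

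**All six antigens.** This treats the comparisons as independent, as the plan does, with influenza at 55% and n = 680. Power is 0.9804³ × 0.9955³ = 93.0% with polio n = 680, and at most 0.9804³ × 0.9985³ = 93.8% with polio n = 800.

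**Selection.** Let e be the share excluded in an arm and q the response among excluded children, with true response 75% in both arms. The retained rate is (0.75 − e·q)/(1 − e). Equal e gives no shift in the difference. With e = 8% against 5% and q = 65%, the rates are 75.87% and 75.53%, a shift of 0.3 points. With e = 10% against 5% and q = 55%, they are 77.22% and 76.05%, a shift of 1.2 points. All these values of e and q are assumed.

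**The case against.** **The effect is negligible and already budgeted for.** This stands as to size. Power is computed on 680 completers, and polio power exceeds 99% either way.

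**A common set is a legitimate choice.** Success requires all six nulls to be rejected together, and the protocol counts a child as fully immunised only after both doses, so one per-protocol set is defensible. But nothing in the design needs it: polio and influenza already use different pairs of groups, and the section already defines a strain-specific influenza subset.

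**The SAP may settle it.** The protocol does not leave the rule open; it states it. The Immunogenicity All Available Population would keep these children, so their data are not lost, but the protocol assigns that population no analysis.

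**Dose 2 and Visit 3 do bear on polio.** A reader might infer that none of the three dose-2 criteria matters for polio. That goes too far. Among children who receive dose 2, the interval and second-draw criteria together supply the only 28–42 day window for the post-OPV sample, so they must be restated and not simply deleted. Also, if the two close-of-study sentences governed, Visit 3 would be the polio time point and group (b) would disappear. The point rests on the one-month interval that the protocol expressly names as primary.

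**Barred children may never be bled.** A reader might infer this because the Visit 2 procedures list the draw under continued eligibility. The Withdrawal criteria already direct continued blood collection where possible, so no change to the visit procedures is proposed. Moving the draw ahead of the eligibility check could also force a second bleed or visit when dose 2 is merely postponed.

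**Conclusion.** The point holds as a minor design improvement. As written, one list tied to dose 2 removes children with a complete primary polio endpoint from the Group 1 versus Group 2 comparisons. The gain from correcting it is at most modest: about 0.08 to 0.23 points of half-width against a 10-point margin, and 0.11 to 0.26 percentage points of power per polio antigen, under the assumed split of losses before and after Visit 2.

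A reader might infer that the polio conclusion is biased or that the trial's power is at risk; the documents support neither. A shift appears only if exclusion is unequal between arms and excluded children respond differently, and nothing in the protocol establishes either. Groups 1 and 2 are also blinded to CAIV-T versus placebo, so knowledge of allocation should not drive unequal exclusion. The case for change is that the exclusion is unnecessary and almost free to remove.

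**What to change.** In the evaluability list of the Data Analysis section, add a separate rule for the three polio endpoints:

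- a draw on the day of dose 1, before dosing;
- receipt of the assigned OPV;
- a second draw 35 ± 7 days after dose 1 and before any dose 2;
- no requirement for dose 2 or for the Visit 3 draw;
- continued exclusion of children given blood products, immunosuppressants or a further OPV dose between the two draws.

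Keep the present four criteria for influenza. In the same section, replace both statements that place the polio measurement at the close of the study with one month after the OPV dose, so that the new rule and the endpoint agree. Leave the Visit 2 procedures as they are.

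The cost is a short addition to the list and two wording corrections, with no extra visit or sample. The downside is that the polio and influenza analysis sets will differ slightly in membership and size, and reports must give both.
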